IMP infusion ^m	X ⁿ	X ^{o,p}																	
AE review	Continuous monitoring																		
Concomitant medications review	Continuous monitoring																		

	BL ^a	Study week																EDV ^b	SFV ^c
		1	2	3	4	5-7	8	9-11	12	13-15	16	17-23	24	25-35	36	37-47	48		
Study day (±2)	1	8	15	22	29	36-50	57	64-78	85	92-120	127	134-162	169	176-246	253	260-330	337		393

BL = baseline; clinESSDAI = clinical; ESSDAI; D = day; d/c = discontinuation; ECG = electrocardiogram; EDV = early discontinuation visit; ESSDAI = EULAR Sjögren’s syndrome disease activity index; ESSPRI = EULAR Sjögren’s Syndrome Patient-Reported Index; EULAR = European Alliance of Associations for Rheumatology; ICF = informed consent form; IgG = immunoglobulin G; IMP = investigational medicinal product; IV = intravenous; MFI = Multidimensional Fatigue Inventory; NA = not applicable; OSS = ocular staining score; PASS = patient acceptable symptom state; PCR = polymerase chain reaction; PD = pharmacodynamics; PGA = patient global assessment; PK = pharmacokinetics; RF = rheumatoid factor; SCR = screening; SFV = safety follow-up visit; SF-36 = 36-Item Short Form Survey; SGUS = salivary gland ultrasonography; SS-A = Sjögren’s syndrome-related antigen A; SS-B = Sjögren’s syndrome-related antigen B; SWSF = stimulated whole salivary flow; UWSF = unstimulated whole salivary flow; W = week.

^a BL will coincide with the final visit of a previous qualifying study. Grayed-out assessments may be conducted as part of the previous qualifying pSS studies.

^b The EDV will be performed within 7 days after last dose administration.

^c Participants will attend a safety follow-up visit 56 ± 3 days after the final IMP administration.

^d Weight mandatory at baseline.

^e Vital signs will be measured before collecting any blood sample or administering IMP infusions.

^f On IMP administration visits, blood samples must be collected predose (preferably within 2 hours before the infusion). On other visits, a blood sample may be collected at any time during the visit.

^h On IMP administration visits, blood samples for PK analyses will be collected predose (preferably within 2 hours before IMP administration). On other visits, a blood sample may be collected at any time during the visit.

ⁱ A PK sample will also be collected within 30 minutes after the end of IMP infusion.

^j The biological domain will remain blinded until the parent study is unblinded.

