8.1. Administrative and Baseline Procedures

The baseline visit for study ARGX-113-2211 will be conducted after the participant has completed the qualifying study. All baseline assessments will be performed before first administration of efgartigimod in ARGX-113-2211, if applicable. Assessments do not need to be repeated if they are performed as part of the last visit of the qualifying study.

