9.3. Statistical Analyses

9.3.1. General Considerations

- Data collected will be listed with derived variables. Descriptive statistical methods will be used to analyze safety and efficacy data
- The results of this study will not be used inferentially
- No formal sample size calculation is presented
- Summaries will include the number of observations (n), mean, SE, 90% CI, median, minimum, and maximum for continuous measures
- Summaries will include sample size, frequencies, and percentages for categorical variables
- The baseline value will be the last assessment before the first administration of the study drug in OLE
- All study visits will be recalculated based on actual dates. The rules for calculating the analysis visits will be documented in the SAP
- Rules for imputing partial dates or missing dates will be provided in the SAP
- Exposure to IMP will be summarized
- TEAEs, AESIs, SAEs, and other safety parameters will be summarized
- AEs will be classified using the latest version of the MedDRA classification system
- AEs, AESIs, and SAEs will be listed corresponding to MedDRA SOC and PT

- Multiple occurrences of a single PT in a participant will be counted only once at the maximum severity/grade
- AEs with missing severity or relationship to IMP will be classified as severe and treatment-related, respectively. All AEs will be summarized by relatedness to IMP
- Any AEs leading to death or discontinuation of IMP will also be summarized
- Population PK/PD analysis may be performed based on the PK and PD data and reported separately
- Laboratory parameters, physical examinations, vital sign measurements, ECG data and PK, PD, immunogenicity, and biomarker results will be summarized descriptively

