6.2. Baseline

Unless otherwise specified, baseline is defined as the last available non-missing measurement from the parent study 2106. Refer to [appendix 1](#) baseline for details. These baseline observations could be either from week 24 or prior visits of ARGX-113-2106. All baseline assessments will be performed before first administration of efgartigimod in ARGX-113-2211, if applicable. The baseline of ECG parameters should come from the same date. If an individual

confidential and proprietary to IQVIA Holdings Inc. and its subsidiaries. Unauthorized use, disclosure or reproduction is strictly prohibited.

ECG parameter is not reported on the latest date prior to 1st IMP infusion within the extension study, leave blank. Assessments do not need to be repeated if they are performed as part of the last visit of the qualifying study. Assessments performed on the same day as the first IMP administration but without time information collected or with time information exactly equal to the time of first IMP administration and which are planned predose will be considered as predose. For parameters related to questionnaires, the baseline is the last value before or at the day of first administration of the IMP, independent of the time of administration. In case the participant never received IMP, the date/time of enrolled will be used instead of first IMP administration date/time. Adverse Events (AEs) and medications commencing on the reference start date will be considered post-baseline unless otherwise indicated based on available start date/time combination or collected electronic case report form (eCRF) information that identifies the individual event/medication as starting prior to first IMP administration.

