6.3. Windowing Conventions

All assessments, including unscheduled assessments, will be allocated to an analysis visit window. Tables and listings will be based on analysis windows defined below. Allocations of assessments will be performed using their relative day.

Table B: Non-efficacy Analysis Visit Definition (immunogenicity)

Phase	Target Day	Assigned Study Day		Week Assigned
		Assigned (Inclusive) From	To	
Treatment	Not applicable ^a			Baseline
	15	1 ^a	22	Week 2
	29	23	43	Week 4
	57	44	71	Week 8
	85	72	99	Week 12
	113	100	141	Week 16
	169	142	211	Week 24
	253	212	295	Week 36
	337	296	Up to the date of SFV.	Week 48
Safety Follow-up	NA	NA	NA	SFV

confidential and proprietary to IQVIA Holdings Inc. and its subsidiaries. Unauthorized use, disclosure or reproduction is strictly prohibited.

^a Last available non-missing measurement from the parent study ARGX-113-2106.

For QW regimen, the final dose will be administrated at week 47. For Q2W regimen, the final dose will be administered at week 46.

After treatment period ends, safety follow-up will be approximately 7 weeks (56 days ± 3 days) will be summarized separately.

[figure not shown]
The above [Table B](#) contains visit window for every assessment's visited (e.g., Immunogenicity). Refer to respective visit window table for other assessments.

Some parameters which are not collected at every visit, visit window will be combined (by extending window with previous or subsequent visits).

[figure not shown]
For e.g. Week 2 are not protocol scheduled visit for brief physical examination (symptom driven), vital signs, electrocardiogram (ECG), clinical laboratory assessments, total IgG, anti-Ro/SS-A, anti-La/SS-B autoantibodies. Hence, visit window can be combined with baseline and week 4. The non-missing value closest to the target day will be used in the analysis in case of multiple observations.

Table B: Non-efficacy Analysis Visit Definition for brief physical examination (symptom driven), vital signs, electrocardiogram (ECG), clinical laboratory assessments, total IgG, anti-Ro/SS-A, anti-La/SS-B autoantibodies.

Phase	Target Day	Assigned Study Day (Inclusive)		Week Assigned
		From	To	
Treatment	Not applicable ^a			Baseline
	29	2	43	Week 4
	57	44	71	Week 8
	85	72	99	Week 12
	113	100	141	Week 16
	169	142	211	Week 24
	253	212	295	Week 36
	337	296	Up to the date of SFV.	Week 48
Safety Follow-up	NA	NA	NA	SFV

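### The SAP's default baseline (latest parent-study value) is inconsistent with the protocol's (latest value before the first OLE dose); the two diverge when a predose value exists only under the OLE, and the difference is undeclared

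*SAP*

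**What the plan says.** **SAP default.** Under SAP 6.2, unless otherwise specified, "baseline is defined as the last available non-missing measurement from the parent study 2106". It continues: "These baseline observations could be either from week 24 or prior visits of ARGX-113-2106". The footnotes to the visit-window tables in SAP 6.3 (Tables B and C) repeat the parent-study source.

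**Protocol rule.** Protocol 9.3.1: "The baseline value will be the last assessment before the first administration of the study drug in OLE". It does not limit which study recorded the value.

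**How the visits fit together.** A note to the Schedule of Activities (Protocol 1.3) says "BL will coincide with the final visit of a previous qualifying study". Protocol 8.1 adds "Assessments do not need to be repeated if they are performed as part of the last visit of the qualifying study", but also foresees baseline work under the extension: "All baseline assessments will be performed before first administration of efgartigimod in ARGX-113-2211, if applicable". SAP 6.2 carries both of these statements over.

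**Exceptions in the SAP.** For questionnaires, "the baseline is the last value before or at the day of first administration of the IMP, independent of the time of administration". ECG baselines must come from a single date, and a parameter not reported on the latest date before the first OLE infusion is left blank. Weight for BMI comes from the OLE baseline (SAP 9.1). SAP 6.2 also counts same-day, planned-predose assessments as predose when the time is missing or equals the dosing time.

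**Declared changes.** SAP 3.4 lists only the dropped biomarker analysis.

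**The concern.** The two definitions can select different records for the same participant and parameter. If a test was missed at parent week 24 but done before dosing on OLE day 1, the protocol uses the day-1 value. The SAP, read literally, goes back to an earlier parent visit. Change from baseline in the OLE would then include change that took place during the parent study, and the measurement closest to the first dose would not be used as the reference.

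The outputs exposed are those under the default rule that need a baseline: laboratory and vital-sign changes and treatment-emergent abnormalities, IgG, RF and autoantibody changes, antidrug antibody (ADA) classification, clinESSDAI change, and the glandular tests. Composites can also mix reference dates. In CRESS and STAR, ESSPRI follows the questionnaire rule, while the serology and glandular items follow the parent-only default.

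**Working it through.** The plan has no sample-size or power figure to reproduce (Protocol 9.5, SAP 3.2), so the check is a comparison of rules.

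**Step 1: apply both rules to the four possible data patterns.**

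| Parent week-24 value | Separate OLE predose day-1 value | SAP 6.2 default, literal | Protocol 9.3.1 | Result |
|---|---|---|---|---|
| Present | None | Week 24 | Week 24 | Same |
| Missing | None | Earlier parent visit | Earlier parent visit | Same |
| Missing | Present | Earlier parent visit | OLE day 1 | Differ |
| Present | Present | Week 24 | OLE day 1 | Differ in source; little effect if same day |

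The SAP gives an older reference in the third row, and in the fourth row only if the dates differ.

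**Step 2: see where an unused day-1 value goes (SAP 6.3).**

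- Laboratory tests, vital signs, ECG, total IgG, anti-Ro and anti-La: first window, days 2 to 43. Day 1 is in no window.
- Urinalysis: first window, days 2 to 141. Day 1 is in no window.
- clinESSDAI: first window, days 2 to 141. Day 1 is in no window.
- Immunogenicity: week 2 window, days 1 to 22. Day 1 is assigned to week 2.

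The schedule includes a baseline ADA sample, and Protocol 8.9 has it drawn before dosing. If post-baseline status is read from the window, a positive predose day-1 sample following a negative parent-study sample would be classed as treatment-induced ADA under SAP 15, Table H. That would add one participant to ADA incidence.

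**Step 3: show that a response can flip (assumed IgG values).** Percent change = 100 × (value − baseline) / baseline, for an on-treatment value of 8.6 g/L:

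- Older parent baseline 9.0 g/L: 100 × (8.6 − 9.0) / 9.0 = −4.4%, which misses the 10% criterion.
- Day-1 baseline 10.0 g/L: 100 × (8.6 − 10.0) / 10.0 = −14.0%, which meets it.

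If the two baselines are exchanged, the flip goes the other way, so the error has no fixed direction. A flipped item changes CRESS or STAR only when it decides whether the threshold is reached.

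**Step 4: size at N = 30.** One changed status moves a proportion by 1/30 = 3.3 percentage points. With exact 90% intervals (lower limit: 5% quantile of Beta(x, n − x + 1); upper limit: 95% quantile of Beta(x + 1, n − x)) and an assumed starting point of 15 responders:

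- 15/30 = 50.0% (33.9 to 66.1)
- 16/30 = 53.3% (37.0 to 69.2), one flip upward
- 18/30 = 60.0% (43.4 to 75.0), three flips upward

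**The case against.** The strongest reply is that in the intended case nothing differs. The OLE baseline visit is the final parent visit, participants roll over at parent week 24 (Protocol 2), SAP 9 ties the baseline visit to that same visit, and completed assessments need not be repeated. This stands, and it confines the problem to exceptions.

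A reader might take the SAP's reference to prior visits as the conflict. It is not: with no OLE value, the protocol rule falls back to the same earlier visit. The conflict lies in restricting the source to the parent study.

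A reader might also infer that every change-from-baseline result and responder definition is affected. The documents do not support that. Questionnaires (including ESSPRI), ECG and weight for BMI have their own rules, and ESSDAI below 5, clinESSDAI below 5 and the CRESS systemic item use no baseline.

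The same-day predose rule suggests that day-1 values were meant to count. That is fair, but the default sentence and the table footnotes say otherwise, so a programmer could implement either. SAP 6.2 also points to Appendix 1 for details; that text was not available, and it may settle the matter.

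On immunogenicity, the day-1 cell carries the baseline footnote mark, so a layout fault is possible. SAP 6.3 also selects the value closest to day 15, so a day-1 sample reaches the week 2 summary only if no closer one exists. Table H, however, uses the highest post-baseline status, so the participant classification lacks that protection.

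**Conclusion.** The two documents give inconsistent default baselines and SAP 3.4 does not say so. The effect is conditional: it needs a predose value recorded only under the OLE, together with a missing parent week-24 value or a week-24 value from a different date. In that case the literal SAP rule uses an older reference for parameters under the default. The day-1 value drops out of the by-visit windows that open on day 2, and a predose ADA sample can be handled as post-baseline.

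It would go too far to say that the SAP overrides the protocol baseline throughout, or that baselines are generally out of date. The number affected is not in the documents and is probably small. If it were two or three of 30 (an assumption), that would be 2/30 = 6.7% to 3/30 = 10.0% of the cohort. How much older the reference would be depends on the parent visit schedule, which is not given. The study is descriptive and tests no hypothesis, so the harm is to the accuracy and reproducibility of the summaries. The correction is still worth making because it costs so little.

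**What to change.** In SAP 6.2, define the default baseline as the latest non-missing value from either study before the first OLE infusion, with an earlier parent visit used only when neither a week-24 nor an OLE predose value exists. Keep the ECG same-date rule and the questionnaire rule as they stand. Align the footnotes to Tables B and C, check Appendix 1 and amend it if needed, and open the immunogenicity week 2 window on day 2.

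If the parent-only rule is intended, list it in SAP 3.4 and report how many baselines, by parameter, predate parent week 24.

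Either route takes a few lines of SAP text, one table cell and a check of the baseline derivation in the programming. No new data are needed.

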6.3. Windowing Conventions

All assessments, including unscheduled assessments, will be allocated to an analysis visit window. Tables and listings will be based on analysis windows defined below. Allocations of assessments will be performed using their relative day.

Table B: Non-efficacy Analysis Visit Definition (immunogenicity)

Phase	Target Day	Assigned Study Day		Week Assigned
		Assigned (Inclusive) From	To	
Treatment	Not applicable ^a			Baseline
	15	1 ^a	22	Week 2
	29	23	43	Week 4
	57	44	71	Week 8
	85	72	99	Week 12
	113	100	141	Week 16
	169	142	211	Week 24
	253	212	295	Week 36
	337	296	Up to the date of SFV.	Week 48
Safety Follow-up	NA	NA	NA	SFV

confidential and proprietary to IQVIA Holdings Inc. and its subsidiaries. Unauthorized use, disclosure or reproduction is strictly prohibited.

^a Last available non-missing measurement from the parent study ARGX-113-2106.

For QW regimen, the final dose will be administrated at week 47. For Q2W regimen, the final dose will be administered at week 46.

After treatment period ends, safety follow-up will be approximately 7 weeks (56 days ± 3 days) will be summarized separately.

[figure not shown]
The above [Table B](#) contains visit window for every assessment's visited (e.g., Immunogenicity). Refer to respective visit window table for other assessments.

Some parameters which are not collected at every visit, visit window will be combined (by extending window with previous or subsequent visits).

[figure not shown]
For e.g. Week 2 are not protocol scheduled visit for brief physical examination (symptom driven), vital signs, electrocardiogram (ECG), clinical laboratory assessments, total IgG, anti-Ro/SS-A, anti-La/SS-B autoantibodies. Hence, visit window can be combined with baseline and week 4. The non-missing value closest to the target day will be used in the analysis in case of multiple observations.

Table B: Non-efficacy Analysis Visit Definition for brief physical examination (symptom driven), vital signs, electrocardiogram (ECG), clinical laboratory assessments, total IgG, anti-Ro/SS-A, anti-La/SS-B autoantibodies.

Phase	Target Day	Assigned Study Day (Inclusive)		Week Assigned
		From	To	
Treatment	Not applicable ^a			Baseline
	29	2	43	Week 4
	57	44	71	Week 8
	85	72	99	Week 12
	113	100	141	Week 16
	169	142	211	Week 24
	253	212	295	Week 36
	337	296	Up to the date of SFV.	Week 48
Safety Follow-up	NA	NA	NA	SFV

Copyright © 2009, 2010, 2012, 2016, 2018, 2019, 2021, 2024 IQVIA. All rights reserved. The contents of this document are confidential and proprietary to IQVIA Holdings Inc. and its subsidiaries. Unauthorized use, disclosure or reproduction is strictly prohibited.

For Urinalysis, we do not have week 2, week 4, week 8, week 12 visit, as in that case the following window:

[figure not shown]
Table B: Non-efficacy Analysis Visit Definition for Urinalysis.

Phase	Target Day	Assigned Study Day (Inclusive)		Week Assigned
		From	To	
Treatment	Not applicable ^a			Baseline
	113	2	141	Week 16
	169	142	211	Week 24
	253	212	295	Week 36
	337	296	Up to the date of SFV.	Week 48
Safety Follow-up	NA	NA	NA	SFV

For Urine pregnancy testing, we only have Baseline, and Safety Follow-up schedules the following window:

Table B: Non-efficacy Analysis Visit Definition for Urine Pregnancy testing.

Phase	Target Day	Assigned Study Day (Inclusive)	Week Assigned
-------	------------	--------------------------------	---------------

Copyright © 2009, 2010, 2012, 2016, 2018, 2019, 2021, 2024 IQVIA. All rights reserved. The contents of this document are confidential and proprietary to IQVIA Holdings Inc. and its subsidiaries. Unauthorized use, disclosure or reproduction is strictly prohibited.

		From	To	
Treatment	Not applicable ^a			Baseline
Safety Follow-up	NA	NA	NA	SFV

^a Last available non-missing measurement from the parent study ARGX-113-2106.

[figure not shown]
For efficacy assessments (e.g., ClinESSDAI), wider window will be considered as follows:

Table C: Efficacy Analysis Visit Definition for ClinESSDAI.

Target Day	Assigned Study Day (Inclusive)		Week Assigned
	From	To	
Not applicable ^a			Baseline
113	2	141	Week 16
169	142	197	Week 24
225	198	239	Week 32
253	240	267	Week 36
281	268	295	Week 40
309	296	323	Week 44
337	324	Until study discontinuation	Week 48

^a Last available non-missing measurement from the parent study ARGX-113-2106.

Note: ClinESSDAI will only be conducted at weeks 32, 36, 40, and 44 if the participant is a non-responder at week 24 and not considered a therapeutic failure by the PI.

Copyright © 2009, 2010, 2012, 2016, 2018, 2019, 2021, 2024 IQVIA. All rights reserved. The contents of this document are confidential and proprietary to IQVIA Holdings Inc. and its subsidiaries. Unauthorized use, disclosure or reproduction is strictly prohibited.

a Last available non-missing measurement from the parent study ARGX-113-2106.

Questionnaires given on the day of the first administration of IMP (pre-administration or post-administration) are allocated to baseline.

Per parameter and analysis window, the non-missing value closest to the target day will be used in the analysis. If more than one non-missing value is located at the same distance from the target day, then the one latest in time will be selected for analysis. The value latest in time will be identified using, in order of preference, the assessment time, and the visit label.

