4. STUDY DESIGN

4.1. Overall Design

Study ARGX-113-2211 is a long-term, single-arm, open-label, multicenter extension of pSS-qualifying efgartigimod studies designed to evaluate the long-term safety of efgartigimod in adult patients with pSS. Participants will be enrolled from both active and placebo arms of qualifying efgartigimod studies and receive efgartigimod IV 10 mg/kg over 48 weeks in the extension study without knowledge of their treatment assigned in the qualifying study. To be eligible to enroll in this study, participants must have completed the treatment period of the qualifying study and must not have permanently discontinued the IMP in that study.

Participants will receive efgartigimod 10 mg/kg by IV infusion either Q2W or QW. The dosing regimen is based on whether the participant is a responder or nonresponder on day 1. Participants will be considered as responders if they have a reduction in clinESSDAI score of ≥ 3 points from baseline (ie, the final visit of a previous qualifying study) and/or a change in score that reclassifies their disease from moderate severity (clinESSDAI ≥ 5) to mild severity (clinESSDAI < 5). Participants will be considered as nonresponders if they do not have a reduction in clinESSDAI score of ≥ 3 points from baseline and/or did not reach a clinESSDAI < 5 . ClinESSDAI assessments to determine responder status using the baseline will be conducted on day 1 and weeks 16 and 24. Responders will receive IV infusions Q2W. Nonresponders will receive an infusion QW until such time that they are considered to be responders. If a participant is not a responder at week 24, they will be evaluated by the PI for therapeutic failure:

- Therapeutic failure - the participant will discontinue study treatment
- Not a therapeutic failure - the participant will continue QW dosing regimen. ClinESSDAI will be conducted at weeks 32, 36, 40, and 44 until confirming responder status and switching to Q2W dosing regimen. The PI will continue to evaluate the participant for therapeutic failure

If the participant and/or investigator consider there to be a reduction in therapeutic effect once the patient has switched to Q2W, the participant will return for an unscheduled visit during which a clinESSDAI, a blood sampling for PK and ADA will be collected.

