9.3.4. Exploratory Endpoints Analysis

To explore the effect of efgartigimod on clinical pSS, glandular measures and patient-reported outcomes, serum and blood biomarkers the following analysis will be performed:

- The proportion along with an exact 90% CI of adjusted CRESS (without serology item) will be presented at week 24 and week 48
- Change from OLE baseline in activity of individual ESSDAI domains score, Hocevar score, Schirmer's test score, OSS score, MFI score, physical component and mental component scores of SF-36, PGA score, individual ESSPRI score, EQ-5D-5L utilities score, VAS score will be summarized descriptively at week 24 and week 48. Observed data will also be summarized at OLE baseline, week 24 and week 48

- Percentage change from OLE baseline scores of SWSF, UWSF will be summarized descriptively at week 24 and week 48. Observed data will also be summarized at OLE baseline, week 24 and week 48
- Observed data for response in salivary gland function and tear gland function (CRESS) and PASS score will be summarized descriptively at OLE baseline, week 24 and week 48
- CCI

- Counts and percentages of number of subjects who are on Q2W and QW dosing regimen will be presented at each scheduled visit
- Counts and percentage of the number of subjects with different clinESSDAI scores will be presented by each scheduled visit and the subgroups
- Time from first infusion to revert to QW dosing regimen will be analyzed using a Kaplan-Meier (KM) method. Summary statistics will include the upper and lower quartiles of duration (days) with 95% confidence interval, median duration (days), 95% confidence interval for median duration (days). KM probability of staying on Q2W dosing regimen will also be presented

All the primary, secondary and exploratory analysis will be based on the FAS.

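### Unscheduled clinESSDAI scores prompted by suspected loss of effect enter the scheduled analysis windows with no priority for scheduled scores, which mainly affects the week 36 and week 16 summaries

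*SAP*

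**What the plan says.** **Windowing (SAP 6.3).** Every assessment goes into a window: "All assessments, including unscheduled assessments, will be allocated to an analysis visit window". These windows drive the outputs: "Tables and listings will be based on analysis windows defined below". The selection rule is "Per parameter and analysis window, the non-missing value closest to the target day will be used in the analysis", and ties go to the later value. Nothing ranks a scheduled score above an unscheduled one. Table C gives the clinESSDAI windows and is introduced with "For efficacy assessments (e.g., ClinESSDAI), wider window will be considered as follows".

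**Who is scored between weeks 24 and 48.** The note under Table C says "ClinESSDAI will only be conducted at weeks 32, 36, 40, and 44 if the participant is a non-responder at week 24", and adds that the participant must not be considered a therapeutic failure. Footnote k of the protocol's Schedule of Activities (SoA) says the same. Under Protocol 4.1 these visits stop once response is confirmed.

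**What prompts an unscheduled score.** When the participant or investigator perceives a loss of effect on Q2W, "the participant will return for an unscheduled visit during which a clinESSDAI, a blood sampling for PK and ADA will be collected" (Protocol 4.1).

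**Where the scores are reported.** SAP 13.1.5 summarises clinESSDAI at weeks 16, 24, 36 and 48, overall and in three dosing-regimen subgroups, and plots mean change with 90% confidence intervals at the same weeks. Other outputs are less specific: box plots without a list of weeks (SAP 13.1.5), clinESSDAI over time by ADA class (SAP 15), and Protocol 9.3.4: "Counts and percentage of the number of subjects with different clinESSDAI scores will be presented by each scheduled visit and the subgroups". Efficacy is analysed on observed data (SAP 13.1), and missing values leave percentage denominators (SAP 7.2).

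**The concern.** In a by-visit summary, a participant's presence in the cell should not depend on how that participant is doing. Here it can. A participant stable on Q2W generates no unscheduled score; one suspected of losing effect does, and the score is then tabulated under a scheduled week as though it were a routine visit. No text requires these values to be marked in the tables or plots.

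The stake is descriptive but real. Protocol 4.3 gives the reason for Q2W as finding out whether spacing doses out preserves the benefit, and the by-visit clinESSDAI tables and curves are what a reader will use to answer that. Week 16 is also the data point at which SAP 4.2 places the interim analysis. With about 30 participants, a few such scores are visible in a cell.

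**Working it through.** The plan gives no power or event figure to reproduce, so the check is on the windows and on who can supply a value.

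**1. Table C rebuilt.** Target day = 7 × week + 1, giving 113, 169, 225, 253, 281, 309 and 337 for weeks 16, 24, 32, 36, 40, 44 and 48. Upper limit = midpoint of adjacent targets: (113+169)/2 = 141, then 197, 239, 267, 295 and 323. All match Table C. Days 198 to 323 are covered without a gap, so any unscheduled score in that span falls in a week 32, 36, 40 or 44 window.

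**2. Week 36 (days 240 to 267).** If the Table C note holds, a week-24 responder has no scheduled clinESSDAI here. An unscheduled score is then the only candidate and is used. The cell holds week-24 nonresponders not yet confirmed as responders, plus those unscheduled scores.

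**3. Size at week 36 (assumptions, not document figures).** N = 30; week-24 responder share 50%, 65% or 80%, leaving 15, 10 or 6 nonresponders; no therapeutic failures; no nonresponder yet confirmed; u unscheduled scores in the window. Share of the cell = u / (nonresponders + u).

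| Nonresponders | u = 1 | u = 2 | u = 4 |
|---|---|---|---|
| 15 | 1/16 = 6% | 2/17 = 12% | 4/19 = 21% |
| 10 | 1/11 = 9% | 2/12 = 17% | 4/14 = 29% |
| 6 | 1/7 = 14% | 2/8 = 25% | 4/10 = 40% |
| Share of all 30 | 3% | 7% | 13% |

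The cell mean moves by share × d, where d is the difference in mean change between the unscheduled scores and the rest of the cell. With d = 3 points (the protocol's response and reversion threshold, used here only as a yardstick), the shift runs from 3 × 1/16 = 0.19 to 3 × 4/10 = 1.2 points.

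**4. Windowing and visit schedule kept apart.** Take u = 0, stable responders averaging a change of −4 and nonresponders 0 (assumed). The week 36 cell mean is 0. The mean over all 30 is −4 × 15/30 = −2.0, −4 × 20/30 = −2.67 or −4 × 24/30 = −3.2. That gap comes wholly from the visit schedule. Taking unscheduled scores out leaves cells of 15, 10 or 6, all week-24 nonresponders.

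**5. Week 16 (days 2 to 141).** The SAP target is day 113; the SoA puts week 16 on day 127, which is 7 × 18 + 1. A scheduled score on day 127 lies 14 days from target. An unscheduled score on day x displaces it when |x − 113| < 14, that is, on days 100 to 126. On day 99 the distances tie and the later, scheduled score stands. If sites instead attend near day 113, the main exposure is a missing scheduled score, which any unscheduled score from day 2 onward could replace. Those at risk before week 16 are participants on Q2W from day 1.

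**6. Weeks 24 and 48.** SoA days 169 and 337 equal the SAP targets, with a ±2-day visit window. An unscheduled score can win only within two days of target or when the scheduled score is missing.

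**7. Is everyone scored at week 36?** The SoA clinESSDAI entry carries footnote k. The ESSDAI row is marked at week 36 without that restriction, and the ESSDAI contains the same 11 clinical domains. SAP 13.1.6 reports STAR at week 36, which needs clinESSDAI. The documents therefore point both ways.

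**The case against.** The strongest reply has five parts.

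- **The study is descriptive.** No hypothesis is tested and the primary objective is safety. This stands, and it limits the weight of the point.
- **The restriction is disclosed, and it is not a windowing effect.** This is correct. A reader might infer that windowing turns weeks 32 to 44 into nonresponder-only cells; the visit schedule does that, and the Table C note says so. Windowing adds only the suspected worseners, which the note does not mention.
- **Weeks 32, 40 and 44 may never be tabulated.** SAP 13.1.5 does not list them for the summaries or mean-change plots. They are affected only if the box plots, the Protocol 9.3.4 counts or the ADA table show them. The SAP's exploratory text is redacted, so nothing can be concluded from it either way.
- **The Q2W subgroup is not made up of worseners.** A reader might infer that its tables describe suspected worseners only and are biased against Q2W. The documents do not support this. A participant who meets the reversion rule returns to QW and belongs to the switched-back subgroup. Nonresponders confirmed as responders at weeks 32 to 44 contribute scheduled scores to the switching-to-Q2W subgroup. That cell is mixed, and no direction can be claimed. In the overall row, however, all unscheduled scores join the nonresponders.
- **Excluding unscheduled scores has its own cost.** A participant who worsens and stops before week 16 could lose the only post-baseline score, a loss that also depends on outcome. This stands and is addressed in the fix.

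It could also be said that SAP 13.1.5 already refers to scheduled timepoints. That phrase names the analysis visit; SAP 6.3 decides what fills it.

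**Conclusion.** The point holds in a limited form. Followed as written, SAP 6.3 places outcome-dependent clinESSDAI values in scheduled cells, unlabelled. Among the named outputs this concerns week 36 and week 16.

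- **Week 36** depends on the Table C note prevailing over the unrestricted ESSDAI row and the STAR output. If everyone is scored at week 36, the effect shrinks to that of weeks 24 and 48. On the assumed counts, unscheduled scores form 6% to 40% of the cell. The true share depends on how many such visits occur, which the documents do not say.
- **Week 16** depends on an unscheduled visit by a participant on Q2W from day 1, together with either a missing scheduled score or a visit held on SoA day 127.
- **Weeks 24 and 48**, where the responder proportions are defined, are largely protected.

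No bias for or against the Q2W subgroup is established. The plan should be changed before database lock, but the primary safety objective is untouched.

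**What to change.** 1. In SAP 6.3, state that by-visit efficacy summaries, plots and counts use scheduled assessments only, and that unscheduled clinESSDAI scores are listed and used for the reversion-to-QW analysis (Protocol 9.3.4). Keep unscheduled values in the safety worst-case derivation (SAP 6.4).
2. Label any clinESSDAI cell at weeks 32 to 44 as week-24 nonresponders still under assessment. Step 1 does not make those cells representative, so the label is needed as well.
3. Reconcile the week 36 ESSDAI row and the week 36 STAR output with the clinESSDAI footnote and the Table C note.
4. Reconcile the week 16 day in the SoA (127) with the SAP target (113).

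The cost is about two SAP sentences plus the reconciliations; steps 1 and 2 change no data collection. The downside is that an unscheduled score can no longer stand in for a missing scheduled one, including for a participant who worsens and stops early. The listing should show those scores, so that the loss is visible.
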